4.2.2 Main Analytical Approach for Primary Endpoint

4.2.2.1 Derivation of ICE's

To facilitate the analysis of the primary endpoint a data set containing all ICEs will be derived. For each participant it will contain a row for each ICE, the date and time of the ICE, the cause/description of the ICE and the categorization into SDCR/NSDCR.

4.2.3 Missing Data and Imputation

Obviously, the optimal strategy for dealing with missing data is to make every effort to obtain complete data during the conduct of the study. The Sponsor will work diligently and use a variety of methods to minimize the percentage of missing data in this trial. Nevertheless, there is likely to be a small percentage of missing data. In this context, approaches to handle missing data for the primary and secondary analysis are described in this section.

If a participant discontinues treatment the Sponsor will ensure all planned assessments are continued whenever possible to avoid unnecessary missingness.

The following missing data and imputation procedure applies to relevant baseline covariates (Stratification factors [auto-antibody type, background therapy and region]) and all longitudinal efficacy scores (MG-ADL, QMG, Myasthenia Gravis Composite [MGC], Myasthenia Gravis Quality of Life [MG-QoL] and Quality of Life in Neurological Disorders [Neuro-QoL]) including baseline.

In the following the resolution of different missingness types are described and will be addressed in the order listed.

4.2.3.1 Lateral Item Missingness

For specific lateral items such as right/Left-hand grip, right/left arm outstretched and right/left leg outstretched one side might be missing when the other is present. In such a case the mean lateral difference across all past visits for the participant will be computed, and the missing item will be imputed based on the contralateral side and the mean lateral difference.

4.2.3.2 Item Missingness

For the efficacy scores (MG-ADL, QMG, MG-QoL, MGC, NeuroQoL) items might be missing. This is the case if at any measurement visit date at least one item has been

recorded. In this case, missing items will be estimated using the proportional method of imputation based on participants' responses to the other items on the questionnaire.

The following rule is applied:

- 1.) If less than 50% of items (number of items available MG-ADL 4, QMG ≤7, MG-QoL ≤8, NeuroQoL: ≤4) are missing, the final score is computed as the sum of the non-missing items times the total number of items divided by the number of non-missing items. As an example, the sum of available items is 6, the number of available items is 9 and the total number of items is 13 then the result is 6*(13/9).
- 2.) In case more items than in the previous instruction are missing then data are considered fully missing and one of the next steps is applied.

The Sponsor will always trust the entered result of the Investigator but might query a site if a result seems incomplete or inconsistent. If a result contains a total score but some items remain incomplete the total score will be used in the statistical analysis. Imputation will only take place if items and total score are missing.

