# Myasthenia Gravis Composite (MGC)

The MGC was developed recently aiming for a simple yet comprehensive measure of MG severity. It was developed by combining items from other MG measures, on the basis of their performance in two clinical trials of mycophenolate in MG (Sanders et al. 2008; Muscle Study Group 2008). The final measure has ten items: two ocular (diplopia and ptosis); four manual muscle test items (facial, neck, shoulder abduction, and hip flexion strength), and four patient-reported items (chewing, swallowing, breathing, and speech). The patient-reported items have to be read to the patients, and the whole scale is completed by the examining investigator. Total scores range from 0 to 50 for which higher scores indicate greater disease severity.

Patients (adult and adolescent patients randomized in the DB period at study start) on AChEI should remain on stable doses throughout the DB period and until Week 12 of the OLE. AChEI should not be taken for at least 10 hours prior to QMG and MG composite testing at each visit (except screening visit), in order to reduce fluctuations in performance on functional tests due to the temporary symptomatic effects associated with AChEI use.

A sample of the MGC questionnaire is included in Appendix 8.

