# Appendix 8 Myasthenia Gravis Composite Scale

Ptosis, upward gaze (physician examination)	>45 seconds=0	11-45 seconds=1	1–10 seconds=2	Immediate=3
Double vision on lateral gaze, left or right (physician examination)	>45 seconds=0	11-45 seconds=1	1-10 seconds=3	Immediate=4
Eye closure (physician examination)	Normal = 0	Mild weakness (can be forced open with effort) = 0	Moderate weakness (can be forced open easily) = 1	Severe weakness (unable to keep eyesclosed) = 2
Talking (patient history)	Normal = 0	Intermittent slurring or nasal speech =2	Constant slurring or nasal but can be understood =4	Difficult to understand speech =6
Chewing (patient history)	Normal = 0	Fatigue with solid food = 2	Fatigue with soft food = 4	Gastric tube = 6
Swallowing (patient history)	Normal = 0	Rare episode of choking or trouble swallowing = 2	Frequent trouble swallowing, e.g., necessitating changes in diet = 5	Gastric tube = 6
Breathing (thought to be caused by MG)	Normal = 0	Shortness of breath with exertion =2	Shortness of breath at rest = 4	Ventilator dependence = 9
Neck flexion or extension (weakest) (physician examination)	Normal = 0	Mild weakness=1	Moderate weakness (i.e., $\sim$ 50% weak, $\pm$ 15% = $3^a$	Severe weakness= 4

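### Two item-missing rules in SAP 4.2.3.2 can give a wrong score: MGC is prorated by item count despite unequal item maxima, and an entered total overrides incomplete items with only an optional query.

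*SAP*

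**What the plan says.** SAP 4.2.3.2 covers five instruments: "For the efficacy scores (MG-ADL, QMG, MG-QoL, MGC, NeuroQoL) items might be missing". If fewer than half the items are missing, "the final score is computed as the sum of the non-missing items times the total number of items", divided by the number answered. If more are missing, the whole score is treated as missing. The formula makes no exception for MGC, and the bracket of item counts gives none for MGC.

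The section then deals with entered totals. "The Sponsor will always trust the entered result of the Investigator but might query a site" when a result looks incomplete or inconsistent. "If a result contains a total score but some items remain incomplete the total score will be used in the statistical analysis". It closes with: "Imputation will only take place if items and total score are missing". So proration is reached only when the total is also blank.

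SAP 4.2.3 applies these procedures to all longitudinal efficacy scores, baseline included. Protocol Appendix 8 lists the ten MGC items with their points and a field for the total. MGC change in AChR+ participants is third in the hierarchy of SAP 4.3.7. A reduction of at least 3 points in MGC and of at least 2 points in MG-ADL are responder endpoints in SAP Table 1.

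**The concern.** Proration by item count fills each blank with the mean of the answered items. That is reasonable when all items share one range, as in MG-ADL, QMG, MG-QOL 15r and Neuro-QoL Fatigue. MGC is a weighted scale. A blank eye-closure item (maximum 2) is filled with the average of heavier items, and the item labelled "Breathing (thought to be caused by MG" (maximum 9) with the average of lighter ones.

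The second rule touches a different set of records. If a site adds up the answered items and enters that sum, each blank counts as zero and the sum is analysed as a full score. The same answers without an entered total would be prorated. The analysed value then depends on whether the total box was filled in. This rule reaches MG-ADL, the primary score. The sensitivity analyses listed in SAP 4.2.4 address rescue therapy, protocol deviations and stopping treatment; none varies the item-level handling.

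**Working it through.** **Inputs.** MGC points from Protocol Appendix 8, in form order (ptosis, double vision, eye closure, talking, chewing, swallowing, breathing, neck, shoulder, hip):

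- Maxima: 3 + 4 + 2 + 6 + 6 + 6 + 9 + 4 + 5 + 5 = 50. This reproduces the 0 to 50 range in SAP 4.3.
- All items mild: 1 + 1 + 0 + 2 + 2 + 2 + 2 + 1 + 2 + 2 = 15.
- All items moderate: 2 + 3 + 1 + 4 + 4 + 5 + 4 + 3 + 4 + 4 = 34.

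The SAP's own example, 6 × 13/9 (= 8.67), confirms the formula: observed sum × total items / answered items.

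**Two formulas for MGC.**

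- Count proration (SAP): observed sum × 10 / number answered.
- Point-weighting: observed sum × 50 / sum of the maxima of the answered items.

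**All items at maximum, one blank.** Eye closure blank: 48 × 10/9 = 53.3. Breathing blank: 41 × 10/9 = 45.6. Point-weighting returns 50 in both cases.

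**One blank, uniform profiles (ten patterns each, equally weighted).**

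| Profile | True total | Mean absolute error, count | Mean absolute error, points | Largest error, count | Largest error, points |
|---|---|---|---|---|---|
| All mild | 15 | 0.67 | 0.38 | 1.67 | 0.85 |
| All moderate | 34 | 1.02 | 0.62 | 2.67 | 2.59 |

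Two moderate examples show that neither formula wins throughout:

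- Eye closure blank: count 33 × 10/9 = 36.67 (error +2.67); points 33 × 50/48 = 34.38 (+0.38).
- Breathing blank: count 30 × 10/9 = 33.33 (error −0.67); points 30 × 50/41 = 36.59 (+2.59).

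**Range check for ordinary patients.** With one blank, exceeding 50 needs an observed sum above 45 (45 × 10/9 = 50). Breathing is scored 0, 2, 4 or 9. With breathing at 4 the full scale reaches at most 45. One blank (eye closure) then gives at most 43 × 10/9 = 47.8. Two blanks (eye closure and ptosis) give at most 40 × 10/8 = 50.0. So with one or two blanks, leaving the range requires breathing answered at 9, which is ventilator dependence.

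**Entered total, MG-ADL (8 items, each 0 to 3).** Every item truly 2, so the true total is 16. One item is blank and the site enters the sum of the other seven:

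- Value used under the SAP: 7 × 2 = 14.
- Same answers with no total entered: 14 × 8/7 = 16.

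The difference of 2 points equals the MG-ADL responder threshold.

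**The case against.** **Safeguards.** Protocol 4.5.8.1 tells site staff to check completed instruments and to have a missing response filled in or confirmed as intended. Protocol 7.1 says that the sponsor will seek clarification of discrepant data. For MGC, "the whole scale is completed by the examining investigator". SAP 4.2.3 expects little missing data. All of this stands and makes the problem records rare. It does not remove the rule: an item confirmed as deliberately blank can still carry a total, and Protocol 7.1 does not say that a total with blank items counts as discrepant. The SAP's permissive wording governs how such a record is scored.

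**The entered total may be right.** Data go from paper forms into the database, so a blank item may be a transcription gap beside a correct total. That is true. It is the reason to ask the site rather than to discard the total.

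**Point-weighting gains little.** Partly accepted. Uniform profiles are artificial. Taking mixed profiles with one random blank, independent items and assumed grade probabilities of 0.30, 0.40, 0.25 and 0.05, the mean absolute error falls only from 1.44 to 1.33. Errors of 3 points or more are slightly more frequent with point-weighting (just under 8% against about 7%).

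**Large errors.** A reader could enumerate all 385 patterns of one to four blanks and report errors of 3 points or more in 37 (all mild) or 96 (all moderate) under count proration, against 0 or 56 under point-weighting. Three or four blanks make up 330 of those patterns and supply all 37 mild errors and 93 of the 96 moderate ones. With one or two blanks the counts are equal: 0 and 0 for mild, 3 and 3 for moderate. Three or four blanks with no total, on a form completed by one investigator, are not a realistic basis for sizing the problem.

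**Conclusion.** The point holds as a minor one. Count proration does not respect the MGC item weights. The entered-total rule can score blanks as zero, in the primary score as well. For a single record with one blank, the MGC error is typically about one point or less in uniform profiles, and the MG-ADL error equals the true grade of the blank item (2 points in the example). The documents give no item-missing rate, so the effect on the trial cannot be derived; it is probably small.

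Three stronger readings are not supported.

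- *That the rules favour satralizumab or create false improvements.* A low score at Week 24 looks like improvement, but a low score at baseline looks like worsening. The rules are the same in both arms and the assessors are blinded. The documents give no reason to expect a bias towards either arm.
- *That MGC scores will often leave the 0 to 50 range.* With one or two blanks this needs ventilator dependence on the breathing item, and MGFA Class V is excluded at entry (Protocol 3.4.2.1).
- *That the bracketed item counts contradict the 50% limit.* The bracket that begins "If less than 50% of items (number of items available MG-ADL 4, QMG" may have lost comparison signs in the PDF text, so no conclusion can be drawn from it. That no count is printed for MGC is a gap worth filling.

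**What to change.** Before unblinding, change SAP 4.2.3.2 as follows.

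1. Prorate MGC as observed sum × 50 / (sum of the maxima of the answered items). Keep count proration for the other four scores. State that MGC needs at least 6 of 10 items answered (fewer than half of 10 missing means at most 4).
2. When a total is entered with incomplete items, require a site query. Use the total if the site confirms that it covers all items, or if no item data exist; otherwise prorate from the items.
3. Amend the last sentence of the section, which limits imputation to records with both items and total missing, to match.

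The cost is three or four sentences in the SAP, one derivation line for MGC and a few extra queries. No new data are needed.

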4.2.3.3 Longitudinal Missingness

In case data are missing for intermediate visits and missingness is not caused by an ICE then data will be imputed based on a missing at random assumption. This imputation will be performed at the same time imputation due to missingness of ICE is performed.

4.2.3.4 Imputation Due to Intercurrent Events

In the following we describe missingness and data imputation due to IECs. A detailed statistical justification for this imputation strategy can be found in Wolbers M et al. (2021).

- 1. For each participant the time of the first ICE is determined using the ICE data set. For each efficacy score a data set is created where all subsequent data to the first ICE is removed. If a participant has multiple ICEs between which normal dosing of study drug is attained all the data are nevertheless removed in a first step, i.e., data that would be dealt under treatment policy is still removed in this step. This ensures that the imputation model is fitted on data that is completely unaffected by ICEs.
- 2. A mixed model repeated measures (MMRM) model is fitted as an imputation model to address all the missingness due to ICEs. The MMRM is modeling change from baseline of the efficacy score (separate MMRMs will be fitted for each score) and has the following covariates: treatment group, visit, treatment group x visit, baseline stratification factors (background therapy, auto-antibody type [where this applies], region), baseline efficacy score and baseline efficacy score x visit. ("x" refers to complete interactions). The MMRM will use an unstructured covariance overall, in case of convergence issues the covariance structure will be simplified to compound symmetry. The resulting model will serve as a model for all imputations of longitudinal data in the next step.

3. The MMRM model implies a multivariate normal imputation distribution conditional on baseline covariates and conditional on observed longitudinal data that is not affected by an ICE. The implied conditional mean of this normal distribution is used to impute missing data. Participants with an ICE but subsequent data available which falls under treatment policy will use the observed data and will not be imputed. Participants on the satralizumab arm with missing data due to an ICE in category SDCR will be imputed using the imputation model and their treatment group covariate will be artificially set to placebo (copy reference imputation), this way their data are imputed as if they had not had a benefit from the treatment after the ICE. This imputation procedure will result in a complete data set for each efficacy score. All the efficacy analyses will be conducted on the completed data sets.

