4.2.1 Definition of Primary Endpoint

The primary endpoint is the difference between the placebo and satralizumab groups in combination with stable background therapy in the change from baseline to Week 24 in the total MG-ADL score in AChR+ participants.

The MG-ADL was developed by Wolfe et al. (1999) to assess the degree of gMG symptoms (six items: diplopia, ptosis, difficulties with chewing, swallowing, talking, and respiratory problems) and functional limitations in carrying out activities of daily living (two items: ability to brush teeth or comb hair and impairment in the ability to arise from a chair) that have been shown to be present and clinically relevant in gMG patients. Each of the eight items is ranked on a 0-3 scale yielding a total score that ranges from 0 to 24, with higher scores indicating greater disease severity (see the Study Protocol, Appendix 6). The items of the MG-ADL were all derived from the original 13-item symptom list that comprises the clinician-rated Quantitative Myasthenia Gravis score (QMG) scale.

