4.3.1.1 ICE Strategies for Estimands for Secondary Endpoints

Endpoints depending on different estimands than the primary will still be computed on the imputed data set of the primary estimand and their ICE strategies will be implemented on top of the imputed data set:

- Responder Estimand: Same imputation as for primary estimand, if a participant requires rescue therapy the participant is categorized as non-responder (composite strategy). For example, for the secondary endpoint percentage of participants with a ≥2-point reduction from baseline in total MG-ADL score at Week 24, the dataset with MG-ADL score imputed as in Section 4.2.3.4. Completed MG-ADL will be used to identify the participants with a ≥2 point reduction from baseline. On top of that, if participants require rescue therapy the participant is categorized as non-responder
- Duration Estimand: Same imputation as for primary estimand, if a participant requires rescue therapy the participant will be imputed as not having an endured treatment effect after administration of rescue therapy (composite strategy).

The following table lists all secondary endpoints, the corresponding estimand, and relevance as secondary endpoint (Table 6). All populations are to be understood as the mITT restricted to the mentioned population. LRP4 & MuSK refers to the AChR- population.

Table 6 Secondary Endpoints and Corresponding Estimand and Relevance

Secondary Endpoint	Population	Relevance	Estimand Type (Generic)	
Mean change from baseline in MG-ADL score at Week 24	OP, LRP4 & MuSK	confirmatory	Primary (continuous) estimand: Difference in mean change of "Score" from baseline in "Population", treated with satralizumab vs placebo, in combination with	
Mean change from baseline in MG-ADL score at Week 24	MuSK	exploratory	stable background therapy, irrespective of taking rescue therapy, treatment discontinuation due to SDCR, as though participants with treatment discontinuation due to NSDCR continued treatment and as though participants	
Mean change from baseline in	AChR+, OP	confirmatory	with missing data after SDCR, rescue therapy, treatment interruption due to infection continued with placebo.	
QMG score at Week 24	LRP4 & MuSK	exploratory		
Mean change from baseline in	AChR+	confirmatory		
MG-QOL 15r total score at Week 24	OP	supportive		
WOOK 24	LRP4 & MuSK	exploratory		
Mean change from baseline in	AChR+	confirmatory		
MGC total score at Week 24	OP	supportive		
	LRP4 & MuSK	exploratory		

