Mean change from baseline in	AChR+	confirmatory		
Neuro-QoL Fatigue Subscale total score at Week 24	OP	supportive		
total soore at Wook 24	LRP4 & MuSK	exploratory		
	AChR+, OP	supportive		

 Table 6
 Secondary Endpoints and Corresponding Estimand and Relevance

Secondary Endpoint	Population	Relevance	Estimand Type (Generic)
Percentage of participants with a ≥2-point (and more) reduction from baseline in total MG-ADL score at Week 24	LRP4 & MuSK	exploratory	reduction from baseline in Score at Week 24 between participants treated with satralizumab vs placebo, in combination with stable background therapy, as though participants with treatment discontinuation due to NSDCR continued treatment and as though participants with missing data after SDCR, treatment interruption due to infection continued with placebo as though participants receiving rescue therapy were not showing a reduction from baseline.
Percentage of participants with a	AChR+, OP	supportive	
≥3-point (and more) reduction from baseline in QMG score at Week 24	LRP4 & MuSK	exploratory	
Percentage of participants with a	AChR+, OP	supportive	
≥3-point (and more) reduction from baseline in total MGC score at Week 24	LRP4 & MuSK	exploratory	
Proportion of participants who	AChR+, OP	supportive	
have achieved minimal symptom expression (total MG-ADL score of 0 or 1) at Week 24	LRP4 & MuSK	exploratory	
Proportion of participants with at	AChR+, OP	supportive	
least one gMG related exacerbation between baseline and Week 24	LRP4 & MuSK	exploratory	

Duration (# consecutive	AChR+, OP		Duration Estimand: The difference in the mean duration of meaningful improvement at
visits) that participants show at least 2 point reduction from baseline MG-ADL	LRP4 & MuSK	exploratory	Week 24 in population between participants treated with satralizumab vs placebo, in combination with stable background therapy, as though participants with treatment discontinuation due to NSDCR continued treatment and as though participants with missing data after SDCR, treatment interruption due to infection continued with placebo as though
WIG-ADL			participants receiving rescue therapy were not showing a further reduction from baseline.

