AChR = acetylcholine receptor; AChR+ = AChR-antibody seropositive (participants/population); gMG = generalized Myasthenia Gravis; LRP4 = low-density lipoprotein receptor-related protein 4; MG-ADL = Myasthenia Gravis Activities of Daily Living; ; MGC = Myasthenia Gravis Composite; MG-QoL = Myasthenia Gravis Quality of Life; MuSK = muscle-specific kinase; NSDCR = not study drug or condition related; OP = overall population; QMG = Quantitative Myasthenia Gravis score; QoL = quality of life; SDCR = study drug or condition related; Exacerbation = increase of non-ocular MG-ADL item by at least two points from baseline or achieving non-ocular item value of 3 when baseline was below 3.

4.3.2 Secondary Endpoints Under the Primary (Continuous) Estimand Framework

Secondary endpoints falling under the primary estimand framework (Table 6) will be analyzed the same way as the primary endpoint. The ANCOVA model will be analyzed by adjusting for the baseline value of the corresponding score, i.e., QMG change from baseline to 24 weeks will be adjusted for baseline QMG (instead of baseline MG-ADL).

The estimands for the secondary endpoints will be derived on the imputed data set of the primary estimand if the corresponding endpoint is solely based on the raw score.

4.3.3 Secondary Endpoints Under the Responder Estimand

To analyze secondary endpoints under the responder estimand framework (Table 6) each participant will have to be labelled as a responder or non-responder. This is done using the complete data set from the Imputation procedure and by applying the definition of the secondary endpoints. For a rationale on those responder definitions refer to the Study Protocol sections on MG-ADL, QMG and MGC responder definitions, which employ minimum clinically important difference derived in the relevant clinical literature. According to ICE specification of the responder estimand, participants that received rescue therapy will be imputed as non-responders (composite strategy) irrespective of the actual score in the completed data set.

A Cochran-Mantel-Haenszel test over the treatment groups stratifying for baseline stratification factors is the treatment effect estimator for the responder estimand. The estimate is the difference in proportion at Week 24.

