4.3.4 Secondary Endpoints Under the Duration Estimand

The duration estimand is only relevant for the analysis of the number of consecutive visits a participant shows an MG-ADL reduction of at least 2 points from baseline. Based on the completed data set, the first time a participant shows a 2-point or more reduction from baseline, the duration is measured until Week 24 or until the visit when MG-ADL=is no longer reduced by 2 points from baseline MG-ADL. The duration is the difference in weeks between the two visits defining the start and end (or Week 24) of reduction from baseline. If the participant shows a reduction for only one visit, the count is set to 1 week. If the participant required rescue therapy, the count is stopped prior to the visit at which the participant received rescue therapy (composite).

The count variable (the number in weeks by consecutive visits) will be modeled using an ANCOVA adjusting for the same covariates as the imputation model and baseline MG-ADL. The treatment effect estimator is the regression coefficient of the treatment group. The estimate is the difference in the mean duration of meaningful improvement at Week 24.

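### Responder, minimal-symptom and duration cut-offs are applied to a single conditional-mean imputation, which biases the reported proportions slightly; an MG-ADL total of 0 or 1 is also undefined for fractional scores

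*SAP*

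**What the plan says.** SAP 4.2.3.4 fits an MMRM to data unaffected by intercurrent events and completes each efficacy score from it: "The implied conditional mean of this normal distribution is used to impute missing data". Every efficacy analysis uses the completed data. For satralizumab patients whose data are missing after an SDCR event, the mean is taken with the treatment covariate set to placebo (copy reference). Other missing values are imputed under missing at random (MAR).

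The cut-offs follow. SAP 4.3.1.1, on the MG-ADL responder: "Completed MG-ADL will be used to identify the participants with a ≥2 point reduction from baseline". SAP 4.3.3, on labelling responders: "This is done using the complete data set from the Imputation procedure and by applying the definition of the secondary endpoints"; and on the estimator: "A Cochran-Mantel-Haenszel test over the treatment groups stratifying for baseline stratification factors is the treatment effect estimator for the responder estimand". SAP 4.3.4 opens the duration count the same way: "Based on the completed data set, the first time a participant shows a 2-point or more reduction from baseline". SAP Table 6 also lists the proportion who "have achieved minimal symptom expression (total MG-ADL score of 0 or 1) at Week 24".

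The MG-ADL total is a whole number by construction: "Each of the eight items is ranked on a 0-3 scale yielding a total score that ranges from 0 to 24". SAP 4.2.3.2 prorates partly complete questionnaires, and its worked example, 6 × 13/9 = 8.67, is left as a fraction.

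Protocol 6.4.5 specified multiple imputation for responders, following the primary estimand. SAP Appendix 1, which lists changes from the protocol, covers the main analysis only: a direct MMRM is replaced by imputation followed by ANCOVA. It mentions neither multiple imputation nor responders.

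**The concern.** A conditional mean is the right filler when the target is a difference in means. A responder rate is a different target. If a patient's imputed reduction is 1.6 points with residual SD 2.84, the chance of a true reduction of at least 2 is 1 − Φ(0.4/2.84) = 44%, yet the SAP counts that patient as a certain non-responder. At an imputed reduction of 2.4 the chance is 56%, and the patient counts as a certain responder. These errors need not cancel within an arm or between arms.

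At stake are the reported MG-ADL, QMG and MGC responder proportions, the minimal-symptom proportion and the duration result. Minimal symptom expression has a second gap: an imputed or prorated total of 0.4 or 1.3 is neither 0 nor 1, and nothing says how to classify it, so the choice falls to whoever programs the analysis.

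**Working it through.** **Inputs.** From SAP 2.2: mean reductions of 2.3 (placebo) and 4.3 (satralizumab), SD 3.97, 80 per arm, treatment withdrawal 10%. Not in the documents, so assumed: the share of Week 24 scores imputed (10% per arm), the correlation between visits, the visit profile and the timing of dropout. Bias is proportional to the imputed share, so 5% imputed halves every bias figure.

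**The plan's own figure.** n per arm = 2 × (1.96 + 1.036)² × (3.97/2.0)² = 71, or 72 with the t distribution. Dividing by 0.9 for withdrawal gives 79 to 80 per arm, which reproduces the planned 160.

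**Closed form, continuous scale.** Let r be the correlation between the conditional mean and the Week 24 change. The true share reaching a 2-point reduction is Φ((μ − 2)/σ). The share whose conditional mean reaches it is Φ((μ − 2)/(rσ)). At r = 0.7, rσ = 2.78:

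- Satralizumab: Φ(2.3/3.97) = 71.9%, against Φ(2.3/2.78) = 79.6%.
- Placebo: Φ(0.3/3.97) = 53.0%, against Φ(0.3/2.78) = 54.3%.
- Difference among imputed patients: 18.9 points becomes 25.3. With 10% imputed, the trial difference moves by 0.10 × (25.3 − 18.9) = 0.6 point.

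**Simulation on whole scores.** Seven visits; rounded normal changes; means flat or ramping over 12 weeks; last observed visit uniform over visits 1 to 6; true model parameters. True rates before the rescue rule are Φ(0.8/3.96) = 58.0% and Φ(2.8/3.96) = 76.0%. Each imputation rule is compared with its own target: the actual score under MAR, and the placebo-based distribution for satralizumab under copy reference. Bias in the MG-ADL 2-point responder difference, in percentage points at 10% imputed:

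| Scenario | MAR | Copy reference |
|---|---|---|
| Compound symmetry 0.5–0.9 | +0.1 to +1.0 | +0.1 to +0.8 |
| Compound symmetry 0.3 | up to +1.8 | up to +1.3 |
| AR(1) 0.3–0.9 | -0.9 to +1.3 | +0.3 to +1.0 |
| Dropout only after no improvement at last visit, all correlations | -0.5 to +4.8 | -0.3 to +1.0 |

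The first three rows assume non-informative dropout.

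Single-arm errors are larger because the arms partly cancel. Among imputed patients under MAR, satralizumab shows 92.5% responders against a true 76.0% (compound symmetry 0.3), and placebo shows 90.1% against 58.0% (AR(1) 0.3). At 10% imputed, those arm rates move by 1.7 and 3.2 points.

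**Other endpoints.** With an assumed baseline mean of 9 and SD of 2.5, and correlation 0.5 to 0.9, the minimal-symptom difference is understated by 0.05 to 0.7 point over both rules. The duration difference moves by -0.01 to +0.12 week. QMG and MGC responders cannot be sized, because no means or SDs are given for them.

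**Check of the remedy.** Draws rounded to whole scores come within 0.05 point of the true difference under non-informative dropout. Unrounded draws miss it by about 0.1 point. Rounding the single conditional mean without draws still leaves up to 0.7 point at correlation 0.5 to 0.9.

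**The case against.** The strongest reply is about scale. Only missing scores are affected. Patients who stop treatment are asked to stay for assessments, observed data after SDCR events are kept, rescued patients are non-responders whatever their score, and SAP 4.2.3 expects little missing data. The 10% is a treatment-withdrawal rate, not a missing-data rate. One percentage point is 0.8 of a patient in an arm of 80. The simulated 58.0% and 76.0% also leave out the rescue rule and differ from the 50% and 75% that SAP 2.2 assumes for responders. All of this stands and sets the severity. None of it makes the conditional mean a valid filler for a cut-off.

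A reader might infer that every cut-off lacks a rule for fractions. The documents do not support that: reductions of at least 2 or at least 3 points are defined for any number, so 1.6 fails. Only the total of 0 or 1 is ambiguous.

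A reader might also infer that the SAP dropped multiple imputation without saying so. The gap is narrower. SAP 1 gives the SAP precedence for regulatory filings, SAP 4.3.1 openly carries the primary imputation scheme to the secondary endpoints, and Appendix 1 announces a change in imputation strategy. What is missing is a sentence saying that the responder analysis no longer uses multiple imputation.

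Finally, SAP 4.2.3.5 describes a jackknife, and SAP 4.3.1 might extend it to the CMH and duration analyses. Whether it does is unclear. It would correct variance, not this bias.

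**Conclusion.** The point holds at low severity. Applying cut-offs to one conditional-mean completion gives biased proportions. For the MG-ADL 2-point responder difference the bias is roughly 0.1 to 1 point at compound-symmetry correlation 0.5 to 0.9, and about -0.9 to +1.8 points over all correlations tried. This rests on the design means and SD, no rescue rule, an assumed 10% imputed per arm and non-informative dropout. Single-arm rates among imputed patients can be off by more.

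Two stronger readings are not supported. The first is that the method favours satralizumab: size and sign depend on the correlation and dropout pattern, which the documents do not give, and the sign reverses in some scenarios. The second is that confirmatory conclusions are at risk. SAP Table 6 rates the responder and minimal-symptom endpoints as supportive or exploratory, and neither they nor duration appear in the testing order of SAP 4.3.7. In a null simulation with 5% to 10% imputed, the stratified CMH test rejected in 4.4% to 6.1% of runs, against 4.5% to 5.3% with complete data, so no material size inflation is claimed.

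The undefined total of 0 or 1 is a separate drafting gap and needs no assumption.

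**What to change.** - For the responder, minimal-symptom and duration endpoints, replace the single conditional mean with a stated number of draws from the same fitted MMRM, under the same MAR and copy-reference rules. This restores what Protocol 6.4.5 planned for responders.
- Classify within each draw, keep the rescue override, and pool. Name the variance method for the CMH difference and for the duration ANCOVA.
- State one rule for non-integer totals at 0 or 1, including ties: a prorated QMG can land exactly on a half, as in 5 × 13/10 = 6.5. Rounding imputed and prorated totals to whole scores is one option. Apply the same rule at the 2-point and 3-point cut-offs.
- Add one sentence to SAP Appendix 1 on any remaining departure from Protocol 6.4.5.
- Leave the primary and continuous secondary analyses as they are.

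The cost is SAP wording, some run time, and a possible slight change in the supportive responder results in either direction.
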